9.6.3 Demographic and Baseline Characteristics and Other Analysis

The comparability of the vaccination groups for each relevant demographic and baseline characteristic will be assessed using summary tables. No statistical hypothesis tests will be performed on these characteristics. The number and percentage of participants randomized and discontinued from the study and discontinuation reasons will be displayed. Demographic variables (age, race, and gender), baseline characteristics, the number (%) of subjects reporting specific prior medications within 14 days prior to the first vaccination, the number (%) of subjects reporting specific concomitant medications within 14 days following any vaccination, the number (%) of subjects reporting specific prior vaccinations within 30 days prior to the first vaccination, and the number (%) of subjects reporting specific concomitant vaccinations within 30 days following any vaccination will be summarized by vaccination group either by descriptive statistics or categorical tables.

9.7 Interim Analyses

A periodic review of safety and tolerability data across the V114 Phase 3 adult program will be conducted by an independent, unblinded, external DMC. A description of the structure and function of the DMC, along with the timing and content of the safety review, will be outlined in the DMC charter. Information regarding the composition of the DMC is provided in Appendix 1. There are no plans to conduct an interim analysis of unblinded immunogenicity data in this study. However, unblinded immunogenicity data will be made available to the DMC upon request to enable a benefit-risk assessment.

The DMC will serve as the primary reviewer of the results of the ongoing safety reviews and will make recommendations for discontinuation of the study or protocol modifications to an executive committee of the Sponsor (see Appendix 1 for details on the Committees Structure for this study). If the DMC recommends modifications to the design of the protocol or discontinuation of the study, this Executive Oversight Committee (EOC) of the Sponsor (and potentially other limited Sponsor personnel) may be unblinded to results at the intervention level to act on these recommendations. The extent to which individuals are unblinded with respect to ongoing safety reviews will be documented by the external unblinded statistician. Additional logistical details will be provided in the DMC Charter.

Study enrollment is likely to be ongoing at the time of external DMC review. Blinding to intervention assignment will be maintained at all investigational sites. Participant-level unblinding will be restricted to an external unblinded statistician performing ongoing safety reviews. Intervention-level ongoing safety reviews will be provided by the external unblinded statistician to the DMC. Prior to final study unblinding, the external unblinded statistician will not be involved in any discussions regarding modifications to the protocol, statistical methods, identification of protocol deviations, or data validation efforts after the safety reviews.

9.8 Multiplicity

The overall success of the study requires demonstrating success on all 15 pneumococcal serotypes for all 3 pairwise comparisons for V114 lots that are evaluated in the primary immunogenicity objective. Since comparisons are made individually for each of the 15 serotypes and for each pairwise comparison, this approach controls the 2-sided type I error rate at 0.05, and no multiplicity adjustment is required.

No multiplicity adjustments will be made for the safety comparisons.

9.9 Sample Size and Power Calculations

9.9.1 Sample Size and Power for Immunogenicity Analyses

This study will randomize approximately 667 participants to receive each of 3 manufactured lots of V114 (Lot 1, Lot 2, and Lot 3) and 220 participants to receive Prevnar 13™.

For the primary hypothesis, this study has >90% power to demonstrate equivalent immunogenicity across the 3 V114 lots. The power and sample size are based on the following assumptions:

- 90% evaluability rate (approximately 600 evaluable participants per intervention group)
- The underlying serotype-specific OPA GMT ratios for each of the 15 pneumococcal serotypes is 1.0.
- The variabilities for OPA titers in the V114 vaccination groups are the same as those observed in V114-006. That is, the standard deviations of the natural log titers for the 15 pneumococcal serotypes range from 1.33 to 2.24.
- The statistical criterion for equivalence requires the bounds of the 2-sided 95% CI of the OPA GMT ratios to be between 0.50 and 2.0.

9.9.2 Sample Size and Power for Safety Analyses

The probability of observing at least 1 SAE in this study depends on the number of participants vaccinated and the underlying incidence of participants with an SAE in the study population. Calculations below assume that 100% of the randomized participants will be evaluable for safety analyses. There is an 80% chance of observing at least 1 SAE among 2000 participants in V114 group (Lot 1, Lot 2, Lot 3 combined) if the underlying incidence of an SAE is 0.08% (1 of every 1243 participants receiving the vaccine). There is a 50% chance of observing at least 1 SAE among 2000 participants in the V114 group if the underlying incidence of an SAE is 0.03% (1 of every 2885 participants receiving the vaccine). If no SAEs are observed among 2000 participants, this study will provide 97.5% confidence that the underlying percentage of participants with an SAE is <0.18% (1 in every 542 participants) in the V114 group (Lot 1, Lot 2, Lot 3 combined).

Table 6 summarizes the percentage point differences between the 2 vaccination groups that could be detected with 80% probability for a variety of hypothetical underlying incidences of an AE.

Table 6 Differences in the Incidence of Adverse Event Rates Between the 2 Vaccination Groups That Can be Detected With an Approximately 80% Probability

Incidence of Adverse Event		Risk Difference
V114 (%) N=2000	Prevnar 13™ (%) N=220	Percentage Points
1.5	0.1	1.4
5.4	2.0	3.4
9.9	5.0	4.9
16.5	10.0	6.5
22.5	15.0	7.5
28.3	20.0	8.3
39.3	30.0	9.3

The incidences presented here are hypothetical and do not represent actual adverse experiences in either group. The incidences assume a 2-sided 5% alpha level, with sample sizes of 2000 participants in the V114 group (Lot 1, Lot 2, Lot 3 combined) and 220 participants in the Prevnar 13™ group. No multiplicity adjustments were made.
 The calculations are based on an asymptotic method proposed by Farrington and Manning (1990) [Farrington, C. P. 1990].

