4 STUDY DESIGN

4.1 Overall Design

This is a randomized, active-controlled, parallel-group, multi-site, double-blind/mask study of V114 in adults 50 years of age or older.

Approximately 2220 participants will be randomized in a 3:3:3:1 ratio to 1 of 4 vaccination groups (approximately 667 participants per V114 arm and 220 participants in the Prevnar 13™ arm): V114 Lot 1, V114 Lot 2, V114 Lot 3, and Prevnar 13™. Randomization will be stratified by participant age at enrollment (50 to 64 years, 65 to 74 years, and ≥75 years). Approximately 50% of the participants will be ≥65 years of age.

Participants will be followed for solicited injection-site AEs from Day 1 through Day 5 postvaccination and solicited systemic AEs from Day 1 through Day 14 postvaccination. In addition, participants will be followed for non-solicited injection-site and systemic AEs through Day 14 postvaccination. Information for SAEs and deaths, regardless of whether the events are considered to be vaccine related by the investigator, will be collected from the time consent is signed through completion of participation in the study. An external Data Monitoring Committee (DMC) will conduct a periodic review of safety and tolerability data for the adult V114 Phase 3 program. A description of the structure and function of the DMC, along with the timing and content of the safety reviews will be outlined in the DMC charter. Information regarding the composition of the DMC is provided in Appendix 1.

Blood samples for immunogenicity assays will be drawn immediately before V114 or Prevnar 13™ vaccination at Visit 1 (Day 1) and at 30 days postvaccination at Visit 2 (Day 30).

After completion of OPA and electrochemiluminescence (ECL) testing, serum samples will be stored to conduct any additional study-related testing as required by regulatory agencies or the Sponsor. Leftover sera from the study may be used for the development and/or validation of pneumococcal assays after completion of all study-related immunogenicity testing; this applies only to sera received from study participants who provided consent for future biomedical research.

In countries that recommend sequential administration of Prevnar 13™ followed at least 12 months later by PNEUMOVAX™23, PNEUMOVAX™23 will be administered outside of this study protocol.

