9.6.2 Statistical Methods for Safety Analyses

Safety and tolerability will be assessed by clinical review of all relevant parameters, including AEs and postvaccination temperature measurements.

Consistency of the safety profile across lots will be assessed via point estimates and 95% CIs (for select safety endpoints) within each of the V114 vaccination groups (Lot 1, Lot 2, Lot 3). Details will be provided in the sSAP. The analysis of safety will then be performed for V114 overall (combining the Lot 1, Lot 2, and Lot 3 vaccination groups) versus the Prevnar 13™ vaccination group following a tiered approach as detailed below (Table 5).

The tiers differ with respect to the analyses that will be performed. AEs (specific terms as well as system organ class [SOC] terms) are either pre-specified as “Tier 1” endpoints or will be classified as belonging to "Tier 2" or "Tier 3" based on the number of events observed.

Tier 1 Events

Safety parameters or AEs of special interest that are identified a priori constitute “Tier 1” safety endpoints that will be subject to inferential testing for statistical significance with p-values and 95% CIs to be provided for between-treatment differences in the proportion of participants with events; these analyses will be performed using the Miettinen and Nurminen (M&N) method [Miettinen, O. and Nurminen, M. 1985], an unconditional, asymptotic method. For this protocol, solicited injection-site AEs (redness/erythema, swelling, and tenderness/pain) from Day 1 through Day 5 postvaccination and solicited systemic AEs (muscle pain/myalgia, joint pain/arthralgia, headache, and tiredness/fatigue) from Day 1 through Day 14 postvaccination are considered Tier 1 events.

Tier 2 Events

Tier 2 parameters will be assessed via point estimates with 95% CIs provided for differences in the proportion of participants with events (also via the M&N method) [Miettinen, O. and Nurminen, M. 1985].

Membership in Tier 2 requires that at least 36 participants in the V114 combined group (combining Lot 1, Lot 2, and Lot 3 vaccination groups) or 4 participants in the Prevnar 13™ group exhibit the event. Because many 95% CIs for Tier 2 events may be provided without adjustment for multiplicity, the CIs should be regarded as a helpful descriptive measure to be used in review, not a formal method for assessing the statistical significance of the between-group differences in AEs.

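### As labelled, Table 6 does not give about 80% power to detect a V114 excess in adverse events: the first row has 16–27% and the other six 63–78%

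*Combined protocol and SAP*

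**What the plan says.** Section 9.9.2 introduces Table 6 as the percentage-point differences between the two vaccination groups that "could be detected with 80% probability for a variety of hypothetical underlying incidences of an AE". The left-hand incidence column is V114 with N=2000. The right-hand one is headed "Prevnar 13™ (%) N=220". In every row the V114 figure is the larger, and the difference column is V114 minus Prevnar 13™. The footnote repeats the sizes by group, "with sample sizes of 2000 participants in the V114 group (Lot 1, Lot 2, Lot 3 combined) and 220 participants" in the Prevnar 13™ group, and names Farrington-Manning as the method. It adds that "The incidences assume a 2-sided 5% alpha level" and that there was no multiplicity adjustment. There is no allowance for dropout: "Calculations below assume that 100% of the randomized participants will be evaluable for safety analyses".

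The analysis that the table supports is in Section 9.6.2. Combined V114 is compared with Prevnar 13™ by the Miettinen-Nurminen method, with p-values and 95% confidence intervals for Tier 1 (solicited) events and intervals only for Tier 2. For a specific event that was not prespecified, "Membership in Tier 2 requires that at least 36 participants in the V114 combined group" or 4 in the Prevnar 13™ group.

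**The concern.** The first row can be questioned by inspection. An incidence of 1.5% in 2000 people is 30 expected events, against 0.2 expected among 220 people at 0.1%. A split of 30 versus 0 is not significant at the 2-sided 5% level, so a detection probability near 80% is implausible.

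Section 4.2 gives better characterization of V114's safety profile as the reason for including Prevnar 13™. Solicited events, which are primary safety endpoints, receive p-values against it. Table 6 is the only statement of what that comparison can detect, because the SAE probabilities in the same section concern V114 alone. If the table overstates the chance of finding a V114 excess, a non-significant Tier 1 result or an unremarkable Tier 2 interval can be taken as more reassuring than it is, especially for uncommon events.

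**Working it through.** **Inputs (all from Section 9.9.2).** 2-sided alpha 0.05; 2000 on V114 and 220 on Prevnar 13™; 100% evaluable; no multiplicity adjustment; Farrington-Manning method; the seven printed incidence pairs.

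**Formula.** For a null difference of zero, the restricted estimate in Farrington-Manning is the pooled rate. With V114 rate p1 (size n1), Prevnar 13™ rate p2 (size n2) and p̄ = (n1·p1 + n2·p2)/(n1 + n2):

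- SE0 = √[p̄(1 − p̄)(1/n1 + 1/n2)]
- SE1 = √[p1(1 − p1)/n1 + p2(1 − p2)/n2]
- power = Φ[(p1 − p2 − 1.96·SE0)/SE1]

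**Reproducing the printed figure.** Row 1 reaches about 80% only with 220 at the higher rate and 2000 at the lower: p̄ = (220×0.015 + 2000×0.001)/2220 = 0.00239, SE0 = 0.00347, SE1 = 0.00823, and power = Φ[(0.014 − 0.00679)/0.00823] = Φ(0.876) = 80.9%.

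**Row 1 as labelled.** p̄ = (2000×0.015 + 220×0.001)/2220 = 0.01361, SE0 = 0.00823, SE1 = 0.00345, and power = Φ[(0.014 − 0.01613)/0.00345] = Φ(−0.617) = 26.9%.

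**Row 4 as labelled.** p̄ = 0.1586, SE0 = 0.02595, SE1 = 0.02186, and power = Φ[(0.065 − 0.05085)/0.02186] = Φ(0.647) = 74.1%.

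The direction matters because the allocation is about 9:1. As labelled, the pooled rate sits close to the higher V114 rate. This inflates the null variance relative to the variance under the alternative.

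**All rows.** FM is Farrington-Manning. Exact is binomial enumeration of the 2-sided Miettinen-Nurminen score test. Swapped means 220 at the higher rate and 2000 at the lower.

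| Printed V114 vs Prevnar 13™ (%) | FM power, labelled | Exact power, labelled | FM power, swapped | V114 rate for 80%, swapped (FM) | V114 rate for 80%, labelled (FM) | V114 rate for 80%, labelled (exact) |
|---|---|---|---|---|---|---|
| 1.5 vs 0.1 | 26.9 | 16.1 | 80.9 | 1.46 | 2.53 | 2.28 |
| 5.4 vs 2.0 | 62.7 | 65.0 | 79.8 | 5.41 | 6.15 | 6.08 |
| 9.9 vs 5.0 | 69.7 | 70.7 | 79.8 | 9.92 | 10.54 | 10.51 |
| 16.5 vs 10.0 | 74.1 | 74.7 | 80.3 | 16.47 | 16.98 | 16.96 |
| 22.5 vs 15.0 | 75.2 | 75.6 | 79.7 | 22.54 | 22.96 | 22.93 |
| 28.3 vs 20.0 | 76.6 | 76.7 | 79.8 | 28.32 | 28.66 | 28.65 |
| 39.3 vs 30.0 | 78.0 | 78.1 | 79.7 | 39.34 | 39.54 | 39.53 |

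The swapped column rounds to all seven printed V114 rates. The labelled column matches none.

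**Other explanations, labelled sizes, first to last row.** Unpooled variance gives 98.2% down to 81.0%; continuity correction, 8.9% up to 75.6%; a null rate equal to the simple average of the two rates, 67.8% up to 79.3%; a one-sided 0.05 test, 55.3% up to 86.5%. None gives about 80% throughout, and none matches the printed rates.

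**Direct check of row 1.** The score test gives p = 0.067 for 30 versus 0 events, 0.051 for 34 versus 0 and 0.048 for 35 versus 0. With no comparator event (probability 0.999^220 = 0.80), at least 35 V114 events are needed when 30 are expected.

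**Check on the rest of the section.** The SAE statements do reproduce. 1 − 0.2^(1/2000) is 1 in 1243, 1 − 0.5^(1/2000) is 1 in 2885, and 1 − 0.025^(1/2000) is 1 in 542. The fault is confined to Table 6.

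**The case against.** The arithmetic is not in dispute, but five points can be made about its weight.

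- **The cause is inferred.** The documents do not show the calculation. If the incidence columns were interchanged, every number is right for a lower rate under V114 and only the labels are wrong. This stands as to cause. It does not rescue the table, which as labelled states something false.
- **No confirmatory safety test depends on it.** The primary safety objective carries no hypothesis and names no comparison with Prevnar 13™. The only primary hypothesis, lot consistency, is powered separately in Section 9.9.1. This stands, and limits the consequence to interpretation.
- **The worst row matters least in practice.** A specific event at row 1 rates that is not prespecified reaches the 36-participant V114 threshold with probability about 0.16, and 4 Prevnar 13™ events with probability below 0.0001. It would usually fall into Tier 3 with no interval to misread. This is fair, but it also shows that the first row promises detection of a difference that the plan would usually not analyse.
- **The shortfall is modest elsewhere.** At comparator rates of 10% and above, power is 74–78% and the detectable difference moves by 0.2 to 0.5 points. Against a claim of approximately 80%, the last row is marginal. This stands.
- **Observed intervals govern interpretation.** Tier 1 results come with 95% confidence intervals, and Section 9.6.2 calls the Tier 2 intervals descriptive. That reduces the risk of over-reading a null result but does not make a wrong power statement acceptable.

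**Conclusion.** The concern holds. With the sizes as labelled, no row of Table 6 reaches 80% power. Power is 16% (exact) to 27% (asymptotic) in the first row, and by Farrington-Manning 63–78% in the others. The difference that can be detected with 80% probability is about 2.4, 4.2, 5.5, 7.0, 8.0, 8.7 and 9.5 points, against the printed 1.4, 3.4, 4.9, 6.5, 7.5, 8.3 and 9.3. The first entry is understated by about 42% on the asymptotic figure (1.4 against 2.43) and 36% on the exact one (1.4 against 2.18). The error is serious for uncommon events and small at high incidences.

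The result rests only on inputs stated in Section 9.9.2 and on a zero-difference null, as a test for any difference requires. An interchange of sizes or columns is the only explanation tried that fits all seven rows, but it remains an inference. Lot-consistency power is unaffected.

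**What to change.** Recompute Table 6 with 2000 attached to the V114 incidence and 220 to the Prevnar 13™ incidence:

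| V114 (%) | Prevnar 13™ (%) | Difference (points) |
|---|---|---|
| 2.3 (exact) | 0.1 | 2.2 |
| 6.2 | 2.0 | 4.2 |
| 10.5 | 5.0 | 5.5 |
| 17.0 | 10.0 | 7.0 |
| 23.0 | 15.0 | 8.0 |
| 28.7 | 20.0 | 8.7 |
| 39.5 | 30.0 | 9.5 |

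Use exact power of the Miettinen-Nurminen test for the 0.1% row and say so in the footnote. The asymptotic answer there (2.5%, difference 2.4) is unreliable with 0.2 expected comparator events. If the table was meant to show detection of a lower rate under V114, keep the numbers, move the V114 (N=2000) heading to the lower-incidence column, and state the direction. A V114 excess would then still need its own table, because at 9:1 allocation the two directions have different power.

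The cost is one corrected table with slightly to moderately less favourable figures. Sample size, analyses and conduct stay as they are.

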9.10 Subgroup Analyses

To determine whether the intervention effect is consistent across various subgroups, the estimate of the between-group treatment effect (with a nominal 95% CI for each V114 vaccination group) will be summarized for the primary immunogenicity endpoint. The 95% CI will only be calculated if there are more than 10 participants in each vaccination group for each subgroup. In addition, a summary of AEs and a summary of solicited AEs will be provided for each subgroup (point estimates only) for V114 overall (combining the Lot 1, Lot 2, and Lot 3 vaccination groups) and the Prevnar 13™ vaccination groups. The following are examples of classification variables:

- Age category (50 to 64 years, 65 to 74 years, and ≥75 years)
- Race (eg, White, Black, Asian, and Other)
- Sex (female, male)

Further details of subgroup analyses will be documented in the sSAP.

9.11 Compliance (Medication Adherence)

Given that participants will receive a single dose of V114 or Prevnar 13™, compliance will not be calculated. However, the number and proportion of randomized participants receiving V114 or Prevnar 13™ will be summarized (Section 9.12).

9.12 Extent of Exposure

The extent of exposure will be summarized by the number and proportion of randomized participants administered V114 or Prevnar 13™.

10 SUPPORTING DOCUMENTATION AND OPERATIONAL CONSIDERATIONS

10.1 Appendix 1: Regulatory, Ethical, and Study Oversight Considerations

10.1.1 Code of Conduct for Clinical Trials

Merck Sharp and Dohme Corp., a subsidiary of Merck & Co., Inc. (MSD)

Code of Conduct for Interventional Clinical Trials

I. Introduction

A. Purpose

MSD, through its subsidiaries, conducts clinical trials worldwide to evaluate the safety and effectiveness of our products. As such, we are committed to designing, implementing, conducting, analyzing and reporting these trials in compliance with the highest ethical and scientific standards. Protection of participants in clinical trials is the overriding concern in the design of clinical trials. In all cases, MSD clinical trials will be conducted in compliance with local and/or national regulations (eg, International Council for Harmonisation Good Clinical Practice [ICH-GCP]) and in accordance with the ethical principles that have their origin in the Declaration of Helsinki.

B. Scope

Highest ethical and scientific standards shall be endorsed for all clinical interventional investigations sponsored by MSD irrespective of the party (parties) employed for their execution (eg, contract research organizations, collaborative research efforts). This Code is not intended to apply to trials that are observational in nature, or which are retrospective. Further, this Code does not apply to investigator-initiated trials, which are not under the full control of MSD.

II. Scientific Issues

A. Trial Conduct

1. Trial Design

Except for pilot or estimation trials, clinical trial protocols will be hypothesis-driven to assess safety, efficacy, and/or pharmacokinetic or pharmacodynamic indices of MSD or comparator products. Alternatively, MSD may conduct outcomes research trials, trials to assess or validate various endpoint measures, or trials to determine patient preferences, etc.

The design (ie, participant population, duration, statistical power) must be adequate to address the specific purpose of the trial. Participants must meet protocol entry criteria to be enrolled in the trial.

2. Site Selection

MSD selects investigative sites based on medical expertise, access to appropriate participants, adequacy of facilities and staff, previous performance in clinical trials, as well as budgetary considerations. Prior to trial initiation, sites are evaluated by MSD personnel to assess the ability to successfully conduct the trial.

3. Site Monitoring/Scientific Integrity

Investigative trial sites are monitored to assess compliance with the trial protocol and general principles of Good Clinical Practice (GCP). MSD reviews clinical data for accuracy, completeness, and consistency. Data are verified versus source documentation according to standard operating procedures. Per MSD policies and procedures, if fraud, scientific/research misconduct, or serious GCP-noncompliance is suspected, the issues

are investigated. When necessary, the clinical site will be closed, the responsible regulatory authorities and ethics review committees notified.

B. Publication and Authorship

Regardless of trial outcome, MSD commits to publish primary and secondary results of its registered trials of marketed products in which treatment is assigned, according to the prespecified plans for data analysis. To the extent scientifically appropriate, MSD seeks to publish the results of other analyses it conducts that are important to patients, physicians, and payers. Some early phase or pilot trials are intended to be hypothesis-generating rather than hypothesis testing, in such cases, publication of results may not be appropriate since the trial may be underpowered and the analyses complicated by statistical issues such as multiplicity.

MSD's policy on authorship is consistent with the recommendations published by the International Committee of Medical Journal Editors (ICMJE). In summary, authorship should reflect significant contribution to the design and conduct of the trial, performance or interpretation of the analysis, and/or writing of the manuscript. All named authors must be able to defend the trial results and conclusions. MSD funding of a trial will be acknowledged in publications.

III. Participant Protection

A. Ethics Committee Review (Institutional Review Board [IRB]/Independent Ethics Committee [IEC])

All clinical trials will be reviewed and approved by an IRB/IEC before being initiated at each site. Significant changes or revisions to the protocol will be approved by the ethics committee prior to implementation, except changes required urgently to protect participant safety that may be enacted in anticipation of ethics committee approval. For each site, the ethics committee and MSD will approve the participant informed consent form.

B. Safety

The guiding principle in decision-making in clinical trials is that participant welfare is of primary importance. Potential participants will be informed of the risks and benefits of, as well as alternatives to, trial participation. At a minimum, trial designs will take into account the local standard of care.

All participation in MSD clinical trials is voluntary. Participants enter the trial only after informed consent is obtained. Participants may withdraw from an MSD trial at any time, without any influence on their access to, or receipt of, medical care that may otherwise be available to them.

C. Confidentiality

MSD is committed to safeguarding participant confidentiality, to the greatest extent possible. Unless required by law, only the investigator, Sponsor (or representative), ethics committee, and/or regulatory authorities will have access to confidential medical records that might identify the participant by name.

D. Genomic Research

Genomic research will only be conducted in accordance with a protocol and informed consent authorized by an ethics committee.

IV. Financial Considerations

A. Payments to Investigators

Clinical trials are time- and labor-intensive. It is MSD's policy to compensate investigators (or the sponsoring institution) in a fair manner for the work performed in support of MSD trials. MSD does not pay incentives to enroll participants in its trials. However, when enrollment is particularly challenging, additional payments may be made to compensate for the time spent in extra recruiting efforts.

MSD does not pay for participant referrals. However, MSD may compensate referring physicians for time spent on chart review to identify potentially eligible participants.

B. Clinical Research Funding

Informed consent forms will disclose that the trial is sponsored by MSD and that the investigator or sponsoring institution is being paid or provided a grant for performing the trial. However, the local ethics committee may wish to alter the wording of the disclosure statement to be consistent with financial practices at that institution. As noted above, all publications resulting from MSD trials will indicate MSD as a source of funding.

C. Funding for Travel and Other Requests

Funding of travel by investigators and support staff (eg, to scientific meetings, investigator meetings, etc.) will be consistent with local guidelines and practices.

V. Investigator Commitment

Investigators will be expected to review MSD's Code of Conduct as an appendix to the trial protocol, and in signing the protocol, agree to support these ethical and scientific standards.

